10.4.2 Analysis of Secondary and Exploratory Immunogenicity Objectives

Immunogenicity of 240 μ g Quad-NIV co-formulated with 75 μ g Matrix-M1 adjuvant, relative to a US-licensed comparator, Fluzone Quadrivalent, based on HAIs (assayed with both egg-propagated virus and wild-type VLP reagents) for all vaccine-homologous influenza A and B strains, and at least 1 antigenically-drifted A or B strain at Day 28 post-vaccination, will be measured in terms of:

- Geometric mean titer (GMT) defined as the antilog of the mean of the log-transformed HAI titers, on Days 0 and 28.
- Geometric mean ratio (GMR) defined as the ratio of post-vaccination to pre-vaccination (Day 0) HAI GMTs (GMR_{Post/Pre}) on Day 28.
- Seroconversion rate (SCR) defined as proportion of subjects in a given treatment group with either a baseline reciprocal (Day 0) titer of < 10 and a post-vaccination reciprocal titer ≥ 40, or a baseline reciprocal (Day 0) titer of ≥ 10 and a post-vaccination titer ≥ 4-fold higher on Day 28.
- Seroprotection rate (SPR) defined as the proportion of subjects with a reciprocal HAI titer ≥ 40 on Day 28.
- Ratio of GMTs between treatment arms at Day 28 post-vaccination (adjusted for intergroup variation in baseline [pre-vaccination] titers).

An additional time-point at Day 182 may also be tested.

Microneutralization (MN) responses at Days 0 and 28 post-vaccination will include:

- GMT defined as the antilog of the mean of the log-transformed neutralizing titer for a given treatment group.
- GMR defined as the ratio of post-vaccination and pre-vaccination neutralizing GMTs within the same treatment group (designated as GMR_{Post/Pre}).
- SCR defined as proportion of subjects in a given treatment group with either a baseline reciprocal titer of < lower limit of quantitation (LLOQ) and a post-vaccination reciprocal titer 4-fold higher than the LLOQ, or a baseline reciprocal titer of ≥ LLOQ and a post-vaccination reciprocal titer ≥ 4-fold higher than the baseline titer.
- Ratio of GMTs between treatment arms at Day 28 post-vaccination (adjusted for intergroup variation in baseline [pre-vaccination] titers).

An additional time-point at Day 182 may also be tested.

Analysis of exploratory CMI response endpoints will be performed on a subset of approximately 140 subjects from several pre-designated clinical sites (70 subjects per treatment arm) and results may be reported as an addendum to the main clinical study report.

10.4.3 Analyses Concerning Safety Objectives

Safety analysis will be descriptive and based on the safety population, defined as all subjects who received a dose of trial treatment. Safety will be summarized overall and by individual treatment arms based on solicited short-term reactogenicity post-injection on Day 0 - 6, 28-day all AE profile by MedDRA preferred term, and 1-year MAE, SAE, and SNMC profiles post-injection on Day 0. All AEs, including MAEs, SAEs, and SNMCs will be tabulated by severity, related (possibly, probably, or definitely vs non-related per investigator assessment), and severe and related. The number and percentage (with 95% CI) of subjects in each treatment group with a given term will be summarized. A listing and narratives of SAEs will also be produced.

10.5 Sample Size Considerations

This study has a single comparison between Quad-NIV and Fluzone Quadrivalent at Day 28 post-vaccination for the primary immunogenicity objective. No adjustment of the Type I error rate for multiple comparisons is warranted since the simultaneous successes of all 8 comparisons planned for the 4 strains contained in the vaccines and the two endpoints (GMT and SCR) are required for the demonstration of the primary non-inferiority objective of the study.

Non-inferiority is defined as the lower bound of the 2-sided 95% CI on the ratio of GMTs (Quad-NIV vs Fluzone) ≥ 0.67 (ie, unadjusted 1-sided p-value < 0.025 against the null hypothesis of H0: Ratio of GMT < 0.67) and the lower bound of the two-sided 95% CI on the difference of the SCRs (Quad-NIV - Fluzone) $\geq -10\%$ (ie, unadjusted 1-sided p-value < 0.025 against the null hypothesis of H0: Difference of SCRs < -10%).

For the calculation of sample size estimation, we used assumptions of true differences, ie, the ratio of GMTs (Quad-NIV vs Fluzone Quadrivalent) is 1.0 for all 4 homologous strains, and

Nanoparticle Influenza	Vaccine, Quadrivalent	Confidential	qNIV-E-301 Protocol
Novavax, Inc.	Version 4	4.0 - 31 October 2019	Page 62

the difference of the SCRs is -2% for each of the 4 homologous strains, based on the average performance in the previous trial (qNIV-E-201). To achieve an overall 90% power (ie, ~ 97.5% power for each of the 4 strains) to demonstrate a non-inferiority margin for SCR difference of -10%, the SCR of reference group (Fluzone Quadrivalent) is assumed to be 0.5 and the SCR of treatment group (Quad-NIV) is assumed to be 0.48 under the null hypothesis of inferiority (H0: Difference of SCRs < -10%). The significance level of the testing is 0.025. Sample size was estimated to be 1195 in each group by assuming equal size in each group. The sample size accounted for a 10% attrition rate for the per-protocol population such that the primary analysis population for all immunogenicity endpoints will be 1325 in each group.

In a previous trial (qNIV-E-201), the observed vaccine-homologous strain-specific standard deviations of log_{10} HAI titers ranged from approximately 0.3 (B/Colorado/06/2017 and B/Phuket/3073/2013) to approximately 0.4 (A/Singapore/INFIMH-16-0019/2016 and A/Michigan/45/2015). The calculated power for each strain, unadjusted for multiple comparisons, is close to 100% to detect a 1.5-fold difference in GMTs. For 4 strains, this study is designed to exclude a GMT ratio of < 0.67 with 100% power. Therefore, for demonstrating non-inferiority for 4 strains with the true ratio of GMTs of 1.0 and the true SCR differences of -2%, this study provides \geq 90% overall power.

For safety endpoints, the probability of observing at least 1 adverse event among 1325 subjects for Quad-NIV is > 90% if the true rate of such events is 0.18%. With 1325 subjects for Quad-NIV, observing no adverse events of interest (eg, vaccine-related SAE) would represent an upper bound of the 1-sided 95% CI on the percentage of such event is 0.2%.

10.6 Plan for Statistical Summaries and Analyses

10.6.1 Day 28 Unblinded Data Review

An unblinded data review will be conducted upon completion of Day 28 visits, which will include all primary endpoints (HAI antibody responses assayed with egg-propagated virus) testing of associated Day 28 serum samples for all 4 vaccine homologous influenza strains (ie, 2 influenza A and 2 influenza B strains) and safety data through Day 28. Data concerning secondary and exploratory endpoints will be included in the unblinded review of Days 0 and 28 as they become available. For the review, treatment codes will only be unblinded after the data are deemed ready for the analysis after all subjects have completed the Day 28 visit and the data are monitored. The determination of the readiness will be based on the blinded review of outstanding queries of critical data points. Given the time-consuming nature of the microneutralization, these data may be presented only in the final CSR or an addendum (see Section 10.6.2).

In order to execute this review, a select group of trial staff will be unblinded at the CRO and at Novavax. All personnel unblinded to the trial data will be documented. No individual unblinded at a subject treatment level will be involved in follow-up safety monitoring. Specifically, personnel at the clinical trial site including, investigators and trial staff, research site, immunology laboratory, and trial subjects will remain blinded to treatment assignments until the end of trial (ie, Day 364).

Nanoparticle Influenza	Vaccine, Quadrivalent	Confidential	qNIV-E-301 Protocol
Novavax, Inc.	Version 4	4.0 – 31 October 2019	Page 63

Since trial procedures and monitoring practices will not change following the review and the trial will not be terminated prematurely on the basis of these data, no decision cut points or stopping rules will be stipulated. Immunogenicity and safety analyses from the unblinded review may be presented in an abbreviated unblinded clinical study report (CSR) drafted by the Sponsor that may be submitted to regulatory authorities as needed.

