Overall, immunogenicity results demonstrated that all Matrix-M1 adjuvanted formulations of Quad-NIV were immunogenic, inducing robust HAI responses against homologous A and B influenza strains, as well as against drifted A/H3N2 strains (A/Switzerland/9715293/2013 and A/Wisconsin/19/2017). Moreover, all Matrix-M1 adjuvanted formulations of Quad-NIV were generally at least comparable to both Fluzone HD and Flublok using the egg-propagated virus or wild-type virus-like particle (VLP) HAI assay formats. Importantly, all Matrix-M1 adjuvanted formulations of Quad-NIV had significantly greater HAI responses compared with Fluzone HD for A/H3N2 strains, both homologous and drifted, as evaluated in the wild-type VLP-based HAI assay. These Quad-NIV formulations were comparable or better than Fluzone HD (not statistically significant) against these same A/H3N2 strains in the egg-propagated assay. Several formulations of Matrix-M1 adjuvanted Quad-NIV were significantly lower for

Nanoparticle Influenza	Vaccine, Quadrivalent	Confidential	qNIV-E-301 Protocol
Novavax, Inc.	Version 4	4.0 – 31 October 2019	Page 27

B/Colorado/06/2017 in the egg-propagated HAI assay compared with Fluzone HD, but remained comparable (ie, no significant difference) in the VLP-based assay. However, it should be noted that both Fluzone HD and Flublok included B/Maryland/15/2016 (a B/Colorado/06/2017-like virus) for the Victoria lineage B strain in their 2018 - 19 vaccine formulations used in this trial, rather than the B/Colorado/06/2017 strain used in the Quad-NIV formulations. While both strains were recommended by WHO as acceptable alternative "like" strains for the B Victoria lineage, the B/Maryland/15/2016 strain systematically induced 2-fold higher HAI antibody responses compared to B/Colorado/06/2017 in ferret studies reported by the CDC and WHO [VRBPAC 2018].

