2.1.2 Secondary Objectives

• To describe the immunogenicity of 240 μg Quad-NIV co-formulated with 75 μg Matrix-M1 adjuvant, and of a US-licensed comparator, Fluzone Quadrivalent, in clinically stable adults ≥ 65 years of age, in terms of HAI (assayed with both egg-propagated virus and wild-type VLP reagents) antibody responses to all Quad-NIV homologous influenza strains (2 influenza A and 2 influenza B strains) and at least 1 antigenically drifted A or B strain in terms of geometric mean titers (GMTs), geometric mean ratio (GMR), seroconversion rate (SCR), seroprotection rate (SPR), and the baseline adjusted ratio of GMTs between treatment arms at Day 28. An additional time-point at Day 182 may be tested by HAI for these outcomes in a subset of subjects in each treatment group.

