 - Pearson Chi-Square p-value will be derived for testing the equality of SCRs between two groups; otherwise Chi-Square p-value will be derived with continuity adjustment if small sample size. The Newcombe method will be used to construct its 95% confidence interval with the following sample SAS code:

```
proc freq data = fludata noprint;
      tables trt*seroconvind / riskdiff (column=2 cl=(newcombe))
      chisq;
run;
```

7.2 **Analysis of Secondary and Exploratory Immunogenicity Objectives**

Immunogenicity of 240 µg Quad-NIV co-formulated with 75 µg Matrix-M1 adjuvant, relative to a US-licensed comparator, Fluzone Quadrivalent, based on HAIs (assayed with both egg-propagated virus and wild-type VLP reagents) for all vaccine-homologous influenza A and B strains, and at least 1 antigenically-drifted A or B strain at Day 28 post-vaccination, will be measured in terms of:

- Geometric mean titer (GMT) defined as the antilog of the mean of the log-transformed HAI titers, on Days 0 and 28.
- Geometric mean ratio (GMR) defined as the ratio of post-vaccination to pre-vaccination (Day 0) HAI GMTs (GMR_{Post/Pre}) on Day 28.
 - Within-group geometric mean ratio (GMR_{post/pre}) for each arm will be conducted using paired t distribution. A sample SAS code is given below:

```
proc ttest data= fludata alpha=0.05;
      by Treatment Visit;
      PAIRED log(HAI D28) *log(HAI D0);
run;
```

- Seroconversion rate (SCR) defined as proportion of subjects in a given treatment group with either a baseline reciprocal (Day 0) titer of < 10 and a post-vaccination reciprocal titer \geq 40, or a baseline reciprocal (Day 0) titer of \geq 10 and a post-vaccination titer \geq 4-fold higher on Day 28.
 - SCR and corresponding 2-sided exact binomial 95% CIs will be calculated using the Clopper-Pearson method with the following sample SAS code:

```
proc freq data=fludata noprint;
      by Treatment;
      tables seroconvind / binomial(exact) alpha=.05;
      output out=out1 binomial;
run;
```

- Seroprotection rate (SPR) defined as the proportion of subjects with a reciprocal HAI titer \geq 40 on Day 28.
 - SPR and corresponding 2-sided exact binomial 95% CIs will be constructed similarly using the Clopper-Pearson method. Chi-Square p-value will be derived for testing the equality of SPRs between two groups similarly as SCR described above. The Newcombe method will be used to construct its 95% confidence interval.

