10 PRELIMINARY UNBLINDED AND FINAL ANALYSES

An unblinded analysis will be conducted upon completion of all Day 28 visits, which will include all primary endpoints (HAI antibody responses assayed with egg-propagated virus) testing of associated Day 28 serum samples for all 4 vaccine homologous influenza strains (ie, 2 influenza A and 2 influenza B strains) and safety data through Day 28. Data concerning secondary and exploratory endpoints will be included in the unblinded review of Days 0 and 28 as they become available. For the review, treatment codes will only be unblinded after the data are deemed ready for the analysis after all subjects have completed the Day 28 visit and the data are monitored.

In order to execute Day 28 unblinded data review, a select group of trial staff will be unblinded at the CRO and at Novavax. All personnel unblinded to the trial data will be documented. No individual unblinded at a subject treatment level will be involved in follow-up safety monitoring. Specifically, personnel at the clinical study site including, investigators and study staff, research site, immunology laboratory, and study subjects will remain blinded to treatment assignments until the end of study (ie, Day 364).

Day 364 final analysis will be conducted when all immunogenicity and safety data through Day 364 have been entered, reviewed, and all queries related to the data have been addressed. Immunogenicity data required prior to the Day 364 analysis will include the mandated timepoints (Days 0 and 28) for the primary and secondary endpoints, with the latter including the four vaccine-homologous A and B strain(s) and at least one antigenically-drifted influenza strains for HAI antibody titers assayed with both egg-propagated virus and wild-type VLP reagents. Immunogenicity data required prior to the Day 364 analysis will also include HAI antibody response at additional time-point Day 182 tested with a subset of subjects pursuant to secondary endpoints. Testing of additional antigenically-drifted influenza strain responses by HAI, and also Microneutralization (MN) and cellular response testing pursuant to the exploratory objectives may be completed later and included in addenda to the study report.

Immunogenicity and safety analyses from the Day 28 unblinded analysis may be presented in an abbreviated Unblinded clinical study report (CSR) drafted by the Sponsor that may be submitted to regulatory authorities as needed.

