12 DATA HANDLING CONVENTIONS

All output will be incorporated into Microsoft Word or Excel files, or Adobe Acrobat PDF files, sorted and labeled according to the International Conference on Harmonisation (ICH) recommendations, and formatted to the appropriate page size(s).

All statistical analyses will be 2-tailed and assessed at the 5% significance level. For all analyses, p-value of < 0.05 will be considered statistically significant.

Tabulations will be produced for appropriate demographic, baseline, and safety parameters. For categorical variables, summary tabulations of the number and percentage of subjects within each category (with a category for missing data) of the parameter will be presented. For continuous variables, the number of subjects, mean and standard deviation (SD), median, minimum, and maximum values will be presented.

All references to analysis of GMT will be interpreted as analysis of the log_{10} of titer values or of the reciprocal titers (eg, the reciprocal titer of 1:160 is the number 160) or of concentrations.

The individual immunogenicity titer values recorded as below the LLOQ of the assay will be set to half LLOQ for the purposes of GMT and GMR analyses. The LLOQ values will be provided by corresponding lab or CRO as part of the data transfer.

Medical history and AEs will be coded using MedDRA Version 22.0.

Each parameter will be reported with the below defined decimal numbers in Table 6.

Table 6: Decimal Numbers for Parameters

Parameter	Number of Decimal			
Number of subjects (e.g. N, N1, N2)	0			
Percentage (%)	1			
Mean	1 more decimal than raw data			
Standard Deviation (SD)	1 more decimal than mean			
Median, Min, Max	as same decimal as raw data			
GMT, GMR _{Post/Pre} , their corresponding 95% CIs	1			
Ratio of GMTs, its corresponding 95% CIs	2			
SPR (%), SCR (%), SPR difference, SCR difference, their corresponding 95% CIs	1			
P value for GMR _{Post/Pre} and Ratio of GMTs	3			

Note: For analysis of exploratory CMI response, up to 5 decimal numbers will be presented depending on number of significant digits for each parameter.

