12.3 Multiple Comparisons/Multiplicity

No multiplicity adjustment will be applied for the secondary endpoints.

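### Do the unnamed drifted strains and undefined Day 182 and MN subsets, still open at the Day 28 code release, undermine the secondary results?

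*Protocol*

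**What the plan says.** **Code release.** After all Day 28 visits, a documented group at the sponsor and the CRO sees treatment codes (Protocol 10.6.1, SAP 10). On other results the Protocol says: "Data concerning secondary and exploratory endpoints will be included in the unblinded review of Days 0 and 28 as they become available". Sites, subjects and the immunology laboratory stay blinded to Day 364.

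**Drifted strains.** No strain is named for this trial. The secondary objective asks for one or more (Protocol 2.2, SAP 2.1.2); exploratory superiority covers one or two (Protocol 3.2.3, SAP 2.2.3). SAP 10 requires at least one, by both HAI formats, before the Day 364 analysis. It lets other work finish later in addenda: "Testing of additional antigenically-drifted influenza strain responses by HAI, and also Microneutralization (MN) and cellular response testing".

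**Subsets.** MN may be run on some participants or strains once HAI is complete (Protocol 2.3). For Day 182 HAI, SAP 10 states "Immunogenicity data required prior to the Day 364 analysis will also include HAI antibody response at additional time-point Day 182 tested with a subset", while SAP 2.1.2 has "An additional time-point at Day 182 may be tested by HAI for these outcomes in a subset of subjects in each treatment group". No size or selection rule is given for either subset.

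**Significance.** SAP 12: "For all analyses, p-value of < 0.05 will be considered statistically significant". SAP 7.2, on seroprotection: "Chi-Square p-value will be derived for testing the equality of SPRs between two groups similarly as SCR described above". SAP 12.3: "No multiplicity adjustment will be applied for the secondary endpoints". SAP Table 6 provides for a p-value on the ratio of GMTs.

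**The concern.** Staff who hold the homologous results by arm could, on the text alone, still influence which drifted strains are assayed and which stored sera go into the Day 182 and MN subsets. The results would then be labelled significant at an unadjusted 0.05.

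The sponsor's Phase 2 trial gives the worry some colour. All adjuvanted formulations "had significantly greater HAI responses compared with Fluzone HD for A/H3N2 strains, both homologous and drifted, as evaluated in the wild-type VLP-based HAI assay" (Protocol 1.6.1.2), but the egg-based H3N2 results were not significantly different, and several formulations were significantly lower for B/Colorado by egg HAI. If lineage and assay drive the result, an open choice between a drifted A and a drifted B strain could shape what is reported. At stake would be the credibility of the breadth-of-response claims.

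**Working it through.** **1. The plan's own figure, and whether it depends on this point.** The plan gives no figure for the drifted strains or the subsets. The nearest is 1195 evaluable per group (Protocol 10.5), from seroconversion rates (SCR) of 0.50 and 0.48, a margin of 0.10 and one-sided alpha of 0.025.

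- At 97.5% power per strain: n = (1.96 + 1.96)² × (0.50×0.50 + 0.48×0.52) / 0.08² = 15.37 × 0.4996 / 0.0064, or 1200 per group.
- At 0.90^(1/4) = 97.40% power the same formula gives 1190.

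The stated 1195 lies between. It uses only the four vaccine strains at Day 28. Because all eight comparisons must succeed, the primary type I error stays at or below 0.025 one-sided whatever happens with drifted strains.

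**2. How many p-values a drifted strain carries.** The SCR chi-square test is written in SAP 7.1.1, whose scope is the homologous strains. In SAP 7.2 the SCR receives a within-arm exact interval; only seroprotection (SPR) receives a between-arm p-value. Table 6 adds the ratio of GMTs. That is 2 measures × 2 assays = 4 per strain.

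**3. Chance of a favourable p < 0.05 with no true difference.** Each two-sided 0.05 test has 0.025 in the favourable direction. For k independent tests the chance is 1 − 0.975^k, which is an upper limit for positively correlated normal statistics.

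| Drifted strains | Tests as written | Chance | Tests if SCR were also tested | Chance |
|---|---|---|---|---|
| 1 | 4 | 9.6% | 6 | 14.1% |
| 2 | 8 | 18.3% | 12 | 26.2% |

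For four equally correlated tests, simulation (200,000 draws) gives 8.8%, 7.8%, 6.6% and 4.6% at correlations of 0.3, 0.5, 0.7 and 0.9. These correlations are assumed; the documents give none.

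**4. What naming the strain would change.** A strain named before code release carries the same four tests and the same 9.6%. The 2.5% for a single test is therefore not a fair benchmark. The figures above measure ordinary multiplicity, not the effect of choosing late. No calculation isolates the latter, and the documents offer no input for one.

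**5. Exploratory superiority.** This uses confidence limits, not p < 0.05: the lower limit of the GMT ratio must exceed 1.5 and that of the SCR difference must exceed 10%. Take the larger SD in Protocol 10.5, 0.4 log10, and 1195 per arm, ignoring any gain from baseline adjustment:

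- SE = 0.4 × √(2/1195) = 0.0164
- estimate needed = log10(1.5) + 1.96 × 0.0164 = 0.1761 + 0.0321 = 0.2082
- distance from equality = 0.2082 / 0.0164, about 12.7 standard errors

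Chance alone does not produce such a finding.

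**6. The Phase 2 evidence.** Both drifted strains reported in Protocol 1.6.1.2 were H3N2; no drifted B strain is reported. B/Colorado was a homologous strain, and the same section notes that the comparators carried B/Maryland, which gave 2-fold higher responses in ferrets. Quad-NIV now contains B/Maryland (Protocol 1.4.1). These results also predate this trial, so a list fixed before code release could draw on them equally. The assay is not an open choice: secondary HAI uses both formats.

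**7. Required or optional Day 182 HAI.** The Protocol and SAP 2.1.2 permit the test; SAP 1.4 and 10 make it a condition of the Day 364 analysis. Doing it complies with every passage. Within the visit windows, the Day 182 sample comes (182 − 7) − (28 + 4) = 143 to (182 + 7) − (28 − 4) = 165 days after the Day 28 sample, so it will normally follow the Day 28 review.

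**The case for a change.** The best case for a change is this. Every subject gives Day 182 serum (Protocol 6.1.7), so collection does not define the subset and someone must choose among stored samples. Protocol 7.3 allows archived sera to be re-assayed against other influenza antigens, so the strain list can grow. The sponsor did define the cell-mediated immunity subset: about 140 subjects, namely everyone at pre-designated sites. Unblinded staff are barred only from follow-up safety monitoring. Choosing from an open list is not a deviation, so the duty to describe deviations in the final report would not expose it. The abbreviated Day 28 report may go to regulators. A remedy would cost a paragraph.

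Most of these facts are right, and the gap is real: a reader cannot tell from the plan how many strains will be tried or how the sera will be drawn. The inference is weaker. No passage says that these choices will be made after code release; the documents are silent on the date. The sentence in Protocol 10.6.1 concerns data entering the review, not selection. Laboratory blinding protects the readings though not the selection. Exclusions from the per-protocol population are settled before unblinding (SAP 3.2, 3.4.1.1). Strains beyond the required one, and MN, may be left to addenda, which already sets them apart from the main report. The lack of multiplicity adjustment is declared for the secondary endpoints, so a reader can discount those p-values.

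**Conclusion.** The concern identifies missing detail, not a rule that gives a wrong answer. The strain list, the subset sizes and the draw are matters a trial team ordinarily settles in a laboratory testing plan or programming specification, with a random draw within arm as the obvious default for a subset. They bear only on results the plan itself calls descriptive or exploratory. The primary non-inferiority conclusion, its alpha and its sample size do not move.

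The size on the secondary side is at most a 9.6% chance of a favourable p < 0.05 for one drifted strain and 18.3% for two. This assumes no true difference, four tests per strain and independence; positive correlation lowers it. If analysts also apply the SCR test to drifted strains, the limits are 14.1% and 26.2%. Either way the multiplicity is the same whether the strains are named early or late, so amending the plan would not reduce it. The effect of late selection itself cannot be quantified from the documents. The mismatch over Day 182 HAI is a wording slip that following the SAP resolves. No change to the plan is called for.
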